The Immediate Extent of the Hypoalgesic Effect Following Central

Mobilisations to L3, L4 and L5.

October 27th 2023

Study Protocol

Study Design

The design of the study was a randomised, single-blind, repeated measures, cross-over design, performed in a single-centre environment. Ethical approval was gained from the School of Sport and Exercise Science ethics committee at the University of Worcester (ISES2018RF1). Informed consent was gained from each participant before testing.

Sample and Inclusion Criteria

The study included twenty asymptomatic participants (11 females and 9 males); the mean age of the participants was 21.9 years (±2.67, range 20- 30). A health questionnaire (based on the PARQ) was completed by each participant to establish any contraindications they may have to the experimental procedures, namely the application of vertebral mobilisations. No participants were required to be excluded as none of them had consulted their doctor in the last six months, were taking any medication, had an infection in the past two weeks, had no heart, asthma, diabetes, bronchitis, epilepsy or blood pressure issues, had any current muscle or joint injury, were able to train/exercise normally or knew of any other reason that would preclude them from participating.

Data Collection

Each participant was randomly assigned using a random number generator to the order in which their lumbar vertebral levels were mobilised and to the order of each dermatome level tested for the baseline and all three mobilisation interventions.

Before initiating the experimental procedure, the participant's age, height, and weight were recorded. The participant was instructed to lay on their back, on the plinth and had the five locations for dermatome testing marked with a water-soluble pen. The researchers utilised the method of using participant's finger breadth to establish dermatome testing sites (Gross et al 2015) the dermatome testing sites were based on Keegan and Garrett's dermatome map (Keegan & Garrett, 1948) see Figure 1. From this point forth, the spinal levels will be referred to as L2 or L3, respectively and the corresponding dermatome of the vertebral level will be referred to as DL2 or DL3.

Figure not included due to copyright reasons.

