Figure 1. The dermatome map was established originally by Keegan & Garrett (1948). DL2 landmark-4 participant's finger breadth inferior from ASIS, mid anterior thigh. DL3 landmark-8 participant's finger breadth inferior from DL2 landmark, mid anterior thigh. DL4 landmark- 2 participant's finger breadth superior from the proximal border of the patella, mid-way. DL5 landmark- 4 participant's finger breadth inferior from tibial tuberosity, then 1 participant's finger breadth lateral (so that the landmark is on the tibialis anterior, not tibia). S1 landmark- 1 participant's finger breadth inferior to the lateral malleolus. Adapted and used with permission from Anatomical Record. 1948;102(4):409.

Once these locations were marked on the participant's left leg, a demonstration of the Neuropen® (Owen Mumford, Oxfordshire, UK) was performed on the participant's hand (opposite to the side being tested). Once all this had been completed, baseline measures were taken. Using the Neuropen®, a standardised force of 40g was applied to one of the locations. The participant then received a small piece of card with a vertical 10cm visual analogue scale (VAS) line on it and a pen and was asked to "draw a horizontal line on the scale to indicate how much sensation you feel, 0 being can-not feel anything and 10 being an extremely strong sensation". Following this explanation, the participant was asked if they understood and whether they needed further instruction to complete the VAS card. Once the participant marked the card, the card and pen were collected and stored, this process was repeated with the remaining four locations (these five cards provided the baseline data). A new tip was used for each participant, and a decrease in PPS represents a reduction in pain.

Once baseline measurements were collected by the lead researcher, the participant was asked to turn onto their front; the first (pre-determined) lumbar vertebra was found using the iliac crest as an anatomical landmark for the differentiation test. When the correct vertebra was located, the experimenter pressed record on the laptop connected to the PGD plinth (see Cooper et al (2018) for full details) to record the force applied and calculate the frequency.

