The lumbar vertebra was mobilised using Maitland's vertebral mobilisation method for posterioranterior central vertebral pressures (PACVPs) for four sets of 30 seconds (Pentelka et al 2012) with up to 30s between each, at a grade III amplitude (Maitland et al 2005) and a target rate of 3Hz (Piekarz & Perry 2015) to ensure the total time for testing was less than fifteen minutes in duration, before the opioid system is activated (Beatti et al 2010). Once the fourth 30-second mobilisation had been completed, the researcher pressed stop on the laptop and asked the participant to roll onto their back. Then the next five sets of data were collected following the same procedure implemented for the baseline measures (collected in a different, pre-determined order each time). This process was repeated for the remaining two vertebrae.

Statistical Analysis Plan

A Multivariate Analysis of Variance (MANOVA) for individual levels against baseline and a One-way Analysis of Variance (ANOVA) for the collated (data set reduced to identify effects at either the same vertebral level as treated versus baseline, one, two or three above or below respectively) mobilisation effect including Tukey post hoc tests for both were conducted using IBM SPSS statistics 25, p values less than 0.05 were defined as acceptable. Effect sizes identifying Cohens d (Large 0.8, Medium 0.5, and Small 0.2) and Magnitude Based Inferences (MBI) were also calculated for each a more comprehensive analysis of the data.

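### In the collated one-way ANOVA, four of the seven signed distance classes are not measured after every mobilised level, so contrasts with them mix distance with level and skin site

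*Combined protocol and SAP*

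**What the plan says.** The title sets the question: "The Immediate Extent of the Hypoalgesic Effect Following Central" followed by "Mobilisations to L3, L4 and L5". Under Data Collection, every participant has all three levels mobilised in random order ("This process was repeated for the remaining two vertebrae"). Each participant "had the five locations for dermatome testing marked with a water-soluble pen". The Figure 1 legend places the highest site at DL2 ("DL2 landmark-4 participant's finger breadth inferior from ASIS, mid anterior thigh") and the lowest at S1 ("S1 landmark- 1 participant's finger breadth inferior to the lateral malleolus"). After each mobilisation the same sites are tested again: "Then the next five sets of data were collected following the same procedure implemented for the baseline measures".

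The Statistical Analysis Plan has two analyses. A MANOVA compares individual levels with baseline. A one-way ANOVA is applied to the collated data, described as "data set reduced to identify effects at either the same vertebral level as treated versus baseline, one, two or three above or below respectively". Both have Tukey post hoc tests at 0.05. For the collated ANOVA the plan names no term for level mobilised, test site or participant. It does not say whether raw scores or changes from baseline are collated, and it does not mention that some classes come from only one or two levels.

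**The concern.** The study asks how far the effect extends from the treated segment, and the outermost classes bear most directly on that. The five sites are fixed while the treated level moves, so the classes are not made up alike. The far-above class can be observed only after the lowest treated level and at the highest site. The far-below class can be observed only after the highest treated level and at the lowest site.

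A one-way ANOVA has distance class as its only factor. If one level works better than another, or one skin site responds more than another, that difference appears as a difference between distance classes. The result could be read as an effect that spreads in one direction and fades in the other. This remains even if every score is a change from the same participant's baseline at the same site. Such a change removes differences in starting sensation, but not differences in response between levels or sites.

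**Working it through.** **Inputs.** Levels L3, L4, L5 (title). Sites DL2, DL3, DL4, DL5, S1 (Figure 1 legend). Twenty participants, each with all levels and sites (Sample and Inclusion Criteria; Data Collection). Classes: same, and one, two or three above or below (Statistical Analysis Plan). The plan gives no class counts, effect sizes or SD, so there is no figure of its own to reproduce.

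**Step 1: fill the classes.** Number the sites 2 to 6 (DL2 to S1) and the levels 3 to 5. Signed distance = site − level, with negative values meaning above. Readings = 20 × cells.

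| Class | Level-site cells | Readings | Level missing |
|---|---|---|---|
| Three above | L5-DL2 | 20 | L3, L4 |
| Two above | L4-DL2, L5-DL3 | 40 | L3 |
| One above | L3-DL2, L4-DL3, L5-DL4 | 60 | none |
| Same | L3-DL3, L4-DL4, L5-DL5 | 60 | none |
| One below | L3-DL4, L4-DL5, L5-S1 | 60 | none |
| Two below | L3-DL5, L4-S1 | 40 | L5 |
| Three below | L3-S1 | 20 | L4, L5 |

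The contrast of three above with three below is L5-DL2 against L3-S1: both level and site differ.

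**Step 2: level differences only (assumed).** Let the true fall be 0.25 cm after L3, 0.50 after L4 and 1.00 after L5, identical at every site, with no distance effect.

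- Three above: 1.00
- Two above: (0.50 + 1.00)/2 = 0.75
- One above, same, one below: (0.25 + 0.50 + 1.00)/3 = 0.58 each
- Two below: (0.25 + 0.50)/2 = 0.38
- Three below: 0.25

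The gradient lies wholly in the four incomplete classes. Reversing the level effects reverses it, and equal level effects remove it.

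**Step 3: site differences only (assumed).** Let the fall be 1.0, 0.8, 0.6, 0.4 and 0.2 cm from DL2 to S1, with no level or distance effect.

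- Three above 1.0 and three below 0.2: a spread of 0.8.
- One above (1.0 + 0.8 + 0.6)/3 = 0.8; same (0.8 + 0.6 + 0.4)/3 = 0.6; one below (0.6 + 0.4 + 0.2)/3 = 0.4. The three classes that are complete over levels still show a false gradient, because their sites differ.
- Level added alone: the assumed fall is 1.4 − 0.2 × site number, and site = level + distance. Level and signed distance therefore absorb it exactly. With L3 as reference the fitted value is 1.4 − 0.2 × 3 − 0.2 × distance, that is 1.4 at three above and 0.2 at three below. The spread is now 1.2 instead of 0.8, and false level differences of 0.2 cm (L4) and 0.4 cm (L5) from L3 appear.

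**Step 4: what can be estimated from the 15 cells.**

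| Model | Columns | Rank |
|---|---|---|
| Level + signed distance | 9 | 9 |
| Level + site + signed distance | 13 | 12 |
| Level + site + unsigned distance (0 to 3) | 10 | 10 |

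The first model can be fitted, but step 3 shows that this does not make it unbiased. In the second, one column is redundant because distance is site minus level: the straight above-to-below trend cannot be separated from level and site. The third is fully estimable. Its distance 3 has one L3 cell, one L5 cell and no L4 cell.

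**Step 5: how often the ANOVA would react.** This was simulated with level-only effects flat across sites, 20 participants, independent errors, an assumed SD of 1.5 cm and 1,500 runs per setting. The planned ANOVA rejected in 5% of runs with no level difference, and in 11%, 41%, 78% and 96% when adjacent levels differed by 0.25, 0.5, 0.75 and 1.0 cm. For the step 2 effects the rate is about 25% at SD 1.5 cm (55% at SD 1.0, 15% at SD 2.0).

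**The case against.** **The plan frames the classes against baseline.** Read that way, a fall at DL2 after L5 really is an effect three segments above the treated level, and in step 2 every class has a true fall. This stands: class-versus-baseline results are valid for the cells they contain. Only comparisons between classes mislead, and the Tukey tests make those comparisons.

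**The classes are nominal and no trend test is planned.** True, but a Tukey contrast between two outer classes carries the same mixture without any trend test.

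**The sizes are chosen, not documented.** This stands. The fourfold range in step 2 repeats the fourfold range assumed for the levels. A reader might infer that the collated results are biased; the documents do not show that, because they give no level effects, site effects or SD.

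**Above and below may be pooled.** Step 2 then gives 0.58, 0.58, (0.50 + 1.00 + 0.25 + 0.50)/4 = 0.56 and (1.00 + 0.25)/2 = 0.63 for distances 0 to 3, so the gradient nearly cancels. The plan's wording favours signed classes but does not settle it. Distance 3 would still lack L4.

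**The MANOVA already covers individual levels.** It can supply level-specific results, but it does not adjust the collated comparison.

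**Conclusion.** The point holds as a limit on what the collated contrasts can show. The class structure in step 1 is exact: four of seven signed classes miss at least one level, and the two outermost are single cells. Contrasts involving those four mix distance with level and site. The size of any distortion rests entirely on assumption. It is zero from this source if levels and sites respond alike, and at the assumed level effects of step 2 it is a difference of 0.75 cm (1.00 − 0.25) between the end classes.

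Three stronger readings are tempting and not supported. First, not every class is incomplete: same, one above and one below cover all three levels. Second, those three are still not safe for a directional claim, because their sites differ. Third, adding level to the ANOVA is not a sufficient repair: it handles level differences but can enlarge a false gradient caused by site differences.

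**What to change.** 1. Report two above (L4-DL2, L5-DL3), two below (L3-DL5, L4-S1), three above (L5-DL2) and three below (L3-S1) against same-site baseline, as findings for those cells and not as a general extent.
2. Draw no upward-versus-downward conclusion from the collated contrasts, including one above against one below.
3. If a pooled distance comparison is wanted, analyse same-site change from baseline by unsigned distance (0 to 3) with level, site and participant in the model, and state that distance 3 has no L4 data. This averages above and below and assumes that level and site effects add.
4. Do not rely on adding level alone.

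No new data are needed, since level and site are known for every reading. The cost is a narrower extent claim and, because the plan describes the analyses as already carried out, a modest reanalysis that should be labelled as post hoc.

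### The collated ANOVA compares above and below classes without site or level terms, so a site gradient in response can pass for directional spread

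*Combined protocol and SAP*

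**What the plan says.** The title gives three treated levels, "Mobilisations to L3, L4 and L5". Data Collection has five skin sites marked ("five locations for dermatome testing marked with a water-soluble pen"). The Figure 1 legend lists them as DL2 to DL5 and S1, the last with "S1 landmark- 1 participant's finger breadth inferior to the lateral malleolus". Each site is read once before any mobilisation ("these five cards provided the baseline data") and again after each mobilisation ("This process was repeated for the remaining two vertebrae"). Randomisation covers the order of levels and the order of site testing.

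The Statistical Analysis Plan then names two analyses. One is a MANOVA of individual levels against baseline. The other is a one-way ANOVA of a reduced data set classed as same level versus baseline, or "one, two or three above or below respectively". The clause on this collated analysis reads "mobilisation effect including Tukey post hoc tests for both". No term for skin site, mobilised level or participant is stated for it. The text does not say whether it uses raw scores with a baseline group or change scores.

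**The concern.** The collated analysis is the one that addresses the title question, how far the effect extends. If above and below are separate classes, Tukey testing automatically includes above-versus-below pairs. Those classes are made up of different skin sites. The sites run from the proximal thigh to below the ankle, and nothing in the documents supports an equal response at all of them. A thigh that responds more than an ankle to any lumbar mobilisation would give the same pattern as an effect that spreads upward. A significant Tukey pair could then be read as directional spread when it reflects where the pin was applied.

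**Working it through.** **Inputs.** Levels L3, L4, L5 are coded 3, 4, 5 (title). Sites DL2, DL3, DL4, DL5, S1 are coded 2 to 6 (Figure 1 legend). Placing S1 one step below L5 is an assumption; it agrees with the SAP's maximum of three below (L3 to S1). Every participant supplies all 3 × 5 = 15 post-mobilisation cells and 5 baseline cells. The plan gives no figure of its own to reproduce here.

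**Step 1: the identity.** Signed distance d = site − level in every cell, with negative d meaning above.

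| d | Cells (site after level) | Mean site code |
|---|---|---|
| −3 | DL2 after L5 | 2.0 |
| −2 | DL2 after L4, DL3 after L5 | 2.5 |
| −1 | DL2 after L3, DL3 after L4, DL4 after L5 | 3.0 |
| 0 | DL3 after L3, DL4 after L4, DL5 after L5 | 4.0 |
| +1 | DL4 after L3, DL5 after L4, S1 after L5 | 5.0 |
| +2 | DL5 after L3, S1 after L4 | 5.5 |
| +3 | S1 after L3 | 6.0 |

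Randomising order changes none of this, because each participant still supplies the same 15 cells. Nor does sample size.

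**Step 2: bias in the one-way comparison.** Suppose change from baseline varies by b cm per site, with no spread and no level effect.

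- The six above cells are DL2 ×3, DL3 ×2, DL4 ×1; mean site (6 + 6 + 4)/6 = 2.67.
- The six below cells are DL4 ×1, DL5 ×2, S1 ×3; mean site (4 + 10 + 18)/6 = 5.33.
- False gap, below minus above: (5.33 − 2.67)b = 2.67b.
- Between d = −3 and d = +3: (6 − 2)b = 4b.

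| Assumed b (cm per site) | Average gap (cm) | Extreme gap (cm) |
|---|---|---|
| 0.1 | 0.27 | 0.4 |
| 0.2 | 0.53 | 0.8 |
| 0.3 | 0.80 | 1.2 |
| 0.5 | 1.33 | 2.0 |

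For example, take b = 0.2 with changes of −1.0, −0.8, −0.6, −0.4, −0.2 cm from DL2 to S1. The signed class means from three above to three below are then −1.0, −0.9, −0.8, −0.6, −0.4, −0.3, −0.2 cm. Grouped by unsigned distance, the same values average −0.6 cm at each of 0, 1, 2 and 3.

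**Step 3: what adjustment can recover.** Each model was built as a design matrix with all factors categorical. A contrast is estimable if adding it as a row leaves the rank unchanged. The first four rows use the 15 change-from-baseline cells. The last two use all 20 cells, including baseline.

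| Model | Columns | Rank | Above-versus-below pairs |
|---|---|---|---|
| Site + signed class | 11 | 11 | Estimable (all 21 signed pairs) |
| Level + signed class | 9 | 9 | Estimable (all 21 signed pairs) |
| Site + level + signed class | 13 | 12 | Not estimable (0 of 21 signed pairs) |
| Site + level + unsigned distance | 10 | 10 | Not in the model; all 6 distance pairs estimable |
| Raw scores, constant site effect + level + signed class | 14 | 14 | Estimable |
| As above, with site-specific change | 18 | 17 | Not estimable |

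In the example of Step 2, adding site returns signed-class coefficients of exactly 0. That relies on there being no level trend. Since level = site − d, a level trend of g cm per step, fitted with site alone, enters the signed classes as −g·d.

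With site and level both free, only the linear part of the above-to-below pattern is lost. Contrasts such as f(k) + f(−k) − 2f(0), the symmetric fall-off, and (f(2) − f(−2)) − 2(f(1) − f(−1)), a non-linear asymmetry, remain estimable.

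**The case against.** The strongest reply is that the identity does harm only under conditions. Each site has its own baseline, so resting differences between sites can be removed. The same mobilisation procedure is applied at all three levels, so equal level response is a reasonable working assumption, and with it a site-adjusted signed model estimates every pair. Equal site response would serve as well. All of this stands. What it does not rescue is the analysis as written, which adjusts for neither factor and states neither assumption. Baseline subtraction does not remove a difference between sites in how much they change.

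A reader might infer that the design cannot estimate direction at all. The documents do not support that: the loss of identification needs free trends in both site and level, and it affects only the linear component. A reader might also infer that the plan sets out to claim upward or downward spread. No directional hypothesis is stated, the title asks about extent, and the MANOVA does not use the distance classes. The risk lies in how the above-versus-below Tukey pairs would be read.

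Two further limits are fair. Seven signed classes is the natural sense of the wording but is not explicit. No site gradient is documented, so every size in centimetres is an assumption, and the 4b figure compares two single-cell classes.

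**Conclusion.** The concern holds in conditional form. If the classes are signed, the collated one-way ANOVA confounds direction with skin site. A response gradient of b cm per site gives a false below-minus-above gap of 2.67b on average, or 0.27 to 1.33 cm for assumed b of 0.1 to 0.5 cm. Site adjustment removes this only under equal response across mobilised levels. Where site and level may both have their own trend in change from baseline, no pairwise signed contrast is identified. The ranks and cell counts follow from the design alone, given S1 as the step below L5. The sizes rest on the assumed gradient. The question of extent, meaning fall-off with distance in either direction, is estimable from the data collected.

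**What to change.** Make the main collated analysis change from same-site baseline by unsigned distance 0, 1, 2, 3. These hold 3, 6, 4 and 2 of the 15 cells; with 20 participants, that is 60, 120, 80 and 40 readings. Include site and mobilised level in the model, and treat participant as the repeated-measures unit. Show above and below separately as description. Make no directional claim unless the SAP states the assumption it rests on, either equal response across levels (with site in the model) or equal response across sites. If unsigned classes were meant from the outset, say so.

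The change needs SAP wording, one recode and a refit, with no new data. There are two costs. Upward and downward classes are averaged. The distance contrasts also lose some precision. In units of the error variance of one cell mean, with independent errors of equal variance, the variance of each contrast against distance 0 is:

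| Distance | Unadjusted | With site and level |
|---|---|---|
| 1 | 1/3 + 1/6 = 0.50 | 0.55 |
| 2 | 1/3 + 1/4 = 0.58 | 0.71 |
| 3 | 1/3 + 1/2 = 0.83 | 1.34 |

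The loss is small at distance 1 and largest at distance 3, which rests on two cells.

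### The collated analysis compares repeated, site-unmatched readings by one-way ANOVA and Tukey, and gives no rule for turning the significant distances into an extent

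*Combined protocol and SAP*

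**What the plan says.** The title names the aim as "The Immediate Extent of the Hypoalgesic Effect Following Central" "Mobilisations to L3, L4 and L5". Study Design describes a "randomised, single-blind, repeated measures, cross-over design", and Sample and Inclusion Criteria reports 20 participants. Under Data Collection each participant "had the five locations for dermatome testing marked with a water-soluble pen" (DL2, DL3, DL4, DL5 and S1). One reading per site is taken before any mobilisation ("these five cards provided the baseline data"), and one per site after each of the three mobilisations.

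The Statistical Analysis Plan then regroups the data by distance from the treated level and applies a one-way ANOVA, "one, two or three above or below respectively) mobilisation effect including Tukey post hoc tests for both", with "p values less than 0.05 were defined as acceptable". Cohen's d and Magnitude Based Inferences are added.

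The plan states no participant term and no matching of a reading to the baseline of its own site. It names no primary contrast and no testing order, and it does not say how the significant distances are to be reported as an extent.

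**The concern.** Extent is an ordered idea: the treated level first, then one, two and three levels away. Tukey uses no order, so it can declare two below affected and one below not, or one above affected and the treated level not. With no stated rule, the analyst must choose after seeing the results whether the reach is the farthest significant distance or the last one before the hole.

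The contrasts beneath that pattern are also poorly matched to the design. A one-way model ignores that the same people supply every class. Comparing a class made of one or two sites with an all-site baseline mixes the effect of mobilisation with ordinary differences in sensation between sites. The main result of the study is therefore both loosely defined and open to bias at the far distances, which decide the reach.

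**Working it through.** The documents give no sample-size, power or error-rate calculation to reproduce; only the 0.05 threshold is stated.

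**1. The classes.** Inputs from Data Collection and the title: 20 participants, 3 levels, 5 sites, 1 baseline round.

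| Class | Level-site pairs | Readings (pairs x 20) |
|---|---|---|
| Three above | L5-DL2 | 20 |
| Two above | L4-DL2, L5-DL3 | 40 |
| One above | L3-DL2, L4-DL3, L5-DL4 | 60 |
| Same | L3-DL3, L4-DL4, L5-DL5 | 60 |
| One below | L3-DL4, L4-DL5, L5-S1 | 60 |
| Two below | L3-DL5, L4-S1 | 40 |
| Three below | L3-S1 | 20 |
| Baseline | all five sites | 100 |

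The total is 400 = 20 x 5 x 4.

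**2. The planned threshold.** Eight groups give 8 x 7 / 2 = 28 pairs, 7 of them against baseline. Error df are 400 - 8 = 392. The Tukey critical |t| is 3.05, against 1.97 unadjusted. In the one-way model, the smallest significant difference in SD units is 3.05 x sqrt(1/n + 1/100):
- n = 60: 3.05 x 0.163 = 0.50
- n = 40: 3.05 x 0.187 = 0.57
- n = 20: 3.05 x 0.245 = 0.75

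A true effect of 0.5 SD sits on the threshold for the three nearest classes, so which of them pass is close to chance. Holes are expected there.

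**3. Frequency of holes.** All effects and variances here are assumed.
- Total SD 1, participant share of variance 0 or 0.5, participant-by-site share 0 or 0.2, equal site means, one-way model (4,000 trials per scenario). Uniform effect: 9-28% at 0.3 SD, 41-57% at 0.5, 2-16% at 0.8, 0-2% at 1.0. Declining 0.5/0.4/0.3/0.2: 9-22%. Declining 0.8/0.6/0.4/0.2: 0-8%.
- Reading SD 1.0-1.5 cm, person SD 1.5, person-by-site and person-by-round SD 0.3 each (2,000-3,000 trials). One-way as written: 19-43% over falls of 0.8 cm (reaching one level, two levels or everywhere) and 1.0 cm everywhere. With a within-person error term: 7-27%, 12-43% and 23-54% for 0.8 cm, and 4-38% for 1.0 cm everywhere.

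**4. Site mismatch.** This assumes that baseline pools all sites and that site means run from -0.6 to +0.6 SD. With no effect of mobilisation and a participant share of 0.5, the planned tests declared at least one false distance in 45-54% of trials. Site-matched paired tests, taken in one pre-set chain, stayed near 5% (4.1-5.9% over the scenarios with a true null).

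**5. Ignored pairing.** Each participant contributes the same number of readings to every class, so participant means cancel from the contrasts but stay in the one-way residual. For that component the fault costs power.

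**6. Ordered testing, on matched paired contrasts.**
- Gate at the treated level, then two branches at 0.05 each: family-wise error 8.9-10.7% (1 - 0.95^2 = 9.75% if independent).
- Branches at 0.025 each: 3.9-5.6%.
- One chain on pooled absolute distance: 4.3-6.1%.
- A chain on the plan's own unmatched contrasts, with unequal site means and a true effect at least at the treated level: 39-69%.

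**7. What ordering gains.** For a 0.8 cm fall everywhere, the seven-class plan identified the true reach in 0-21% of trials, against 42-84% for a pooled, paired outward chain. Those procedures differ in pooling, pairing and order together. On the same four pooled distances, order alone added 0 to about 15 points over Tukey and about 0-21 over Holm. With directions kept apart, at reading SD 1.0, the two-branch chain and within-person Tukey gave 21 v 23%, 57 v 61% and 82 v 80% (fall everywhere, two levels, one level). At SD 1.5 the chain gained at most about 10 points.

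**The case against.** The strongest reply is that the test is serviceable and only a sentence is missing. Reading the unbroken run of Tukey-significant distances outward from the treated level yields one extent without raising Tukey's error rate. That is right. A reader might infer that a hole leaves the extent undefinable, or that Tukey must give way to an ordered test; the documents support neither. What is missing is the rule.

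Second, nothing in the documents says the effect must fade with distance. An isolated farther effect could be real, and a gate would suppress it. Extent could also mean size, since effect sizes are planned. This stands as a reason not to impose a sequence, though the collated analysis is organised by distance.

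Third, the plan separates above from below, and pooling them changes the question. With a fall at the treated level and below only, a pooled chain declared a reach of at least one level away in about 35-85% of simulated trials although nothing happened above. This stands too.

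Fourth, the wording leaves room: one-way ANOVA may be shorthand for a repeated-measures model, baseline may be site-specific, and the classes may be four pooled distances. None of these is stated. Four pooled classes under one-way Tukey still left holes in 17-43% of simulated trials.

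**Conclusion.** The concern holds as a gap in specification and matching. The collated analysis takes no account of repeated readings, does not match sites, and has no extent rule. Holes are common at medium effects (41-57% at a uniform 0.5 SD) and rare at large ones (0-2% at 1.0 SD). These rates rest on assumed variances and effects, on seven classes, and on the one-way model as written; the site-mismatch figure also assumes an all-site baseline.

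Three stronger inferences are not supported. The contrast of 0-21% with 42-84% is not the gain from ordering: order alone on the same pooled distances is worth roughly 0-20 points, depending on the comparator. An outward sequence does not automatically hold 5% error, because distance runs in two directions and the tests must be site-matched. Nor does a sequence always deliver a reach: if the treated level fails, the extent is empty. Under the assumed centimetre variances, a uniform 0.5 cm fall gave no extent in 34-61% of trials.

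**What to change.** Replace the collated one-way ANOVA and Tukey tests as follows.

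1. For each participant and each of the seven classes, average the change from the same site's baseline over that class's level-site pairs. Test the 20 averages with a paired error (19 df).
2. Report all seven classes with 95% CIs.
3. Define the extent, separately above and below, as the unbroken run of significant distances outward from the treated level, empty if the treated level is not significant. Base significance on tests adjusted over the seven classes, for example by Holm. An unbroken run read from unadjusted 0.05 tests in both directions is the two-branch procedure with about 10% error.
4. If an ordered test is preferred, use one chain at 0.05 on pooled absolute distance, or two chains at 0.025 each after the treated level passes at 0.05.

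The cost of items 1-3 is SAP wording and a short re-analysis of existing readings. Item 4 costs more: pooling hides direction, separate chains lose most of the power gain, decline with distance is assumed, and an isolated farther effect cannot be claimed. The SAP is in the past tense, so the data appear to be held already. Any sequence or extent rule set now should be labelled post hoc unless it was fixed without sight of the results.
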